7.3.4. SAS codes to run t-test on MI data

```
ods output statistics=ttest1;

proc ttest data=pr2;

by AVISITN IMPUT;

where TRPG1N in (1 3);

class TRPG1N ;

var CHG;
```

run;

Sponsor:	Ocular Therapeutix, Inc.			
Protocol:	CLN-Protocol-0054			
Document Version No.:	V1.0	V1.0 Document Date: 01-OCT-2021		

data ttest2;

set ttest1; if class="Diff (1-2)" and method ne "Pooled" then delete;

run;

ods output parameterestimates=pdiff_ttest; proc mianalyze data=ttest2; modeleffects mean; stderr stderr; by AVISITN CLASS;

run;

7.3.5. SAS codes to run ANCOVA (using PROC MIXED) on MI data

ods output LSMESTIMATEs=LSMESTIMATEs; proc mixed data= pr2; by AVISITN IMPUT; CLASS TRPG1N (ref=last); MODEL CHG=TRPG1N base; Ismeans TRPG1N/ cl pdiff; LSMESTIMATE TRPG1N "1G1" **1000**, "2G2" 0 1 0 0, /* WF1 and WF2 are the sample size weighted coefficient for group 1 and 2 respectively*/ "3G(1/2)" &WF1. &WF2A. 00, "4G3" **0010**, "5G4" 0001, "6G1 vs G3" 10-10, "7G2 vs G3" **01-10**, "8G1 vs G4" **100-1**, "91G2 vs G4" 0 1 0 -1, "92G(1/2) vs G3" &WF1. &WF2A. -10, "93G(1/2) vs G4" &WF1. &WF2A. 0-1 / cl;

run;

proc sort data=LSMESTIMATEs; by AVISITN LABEL;

run;

Sponsor:	Ocular Therapeutix, Inc.			
Protocol:	CLN-Protocol-0054			
Document Version No.:	V1.0	Document Date:	01-OCT-2021	

ods output ParameterEstimates=outIsmean; PROC MIANALYZE DATA=LSMESTIMATEs; modeleffects estimate; stderr stderr; by AVISITN LABEL; RUN;

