4.2. General Statistical Methods and Data Handling

4.2.1. **General Methods**

All output will be incorporated into Microsoft Excel or Word files, sorted, and labeled according to the International Council on Harmonisation (ICH) recommendations, and formatted to the appropriate page size(s).

Tabulations will be produced for appropriate demographic, baseline, efficacy, pharmacokinetic and safety parameters. For categorical variables, summary tabulations of the number of missing, and number and percentage of each category of the parameter will be presented by treatment groups and visits (as applicable). For continuous variables, the n, mean, standard deviation, median, minimum, and maximum values will be presented.

The baseline visit will be defined as the last non-missing measure prior to initiation of investigational treatment. Differences between treatment groups will be calculated as OTX-CSI minus HV, and change from baseline will be calculated as follow-up visit minus baseline visit values.

All statistical testing will be done at the two-sided alpha level of 0.05.

Sponsor:	Ocular Therape	Ocular Therapeutix, Inc.			
Protocol:	CLN-Protocol-0054				
Document Version No.:	V1.0	V1.0 Document Date: 01-OCT-2021			

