4.2.9.1. Imputation Method for Efficacy Endpoints

To impute missing, Markov Chain Monte Carlo (MCMC) multiple imputation (MI), Fully Conditional Specification multiple imputation (FCS MI) and last observation carried forward (LOCF) methods will be used.

For MI, we will have below phases:

1. Imputation Phase: in this phase, the missing data will be imputed using SAS PROC MI and a complete data set will be created. This process of imputation will be repeated 25 times. Therefore, 25 compete datasets will be created. In this phase, treatment group, baseline value, and post-baseline visits from visit 3 to visit 8, respectively, will be included in multiple imputation model.

2. Analysis Phase: each of the 25 complete data sets will be analyzed independently using desired statistical method (e.g. ANCOVA for primary efficacy analysis).

3. Pooling Phase: in this phase the estimates obtained from each analyzed complete dataset from phase 2, will be combined using PROC MIANALYZE.

The analysis of efficacy variables Schirmer Test, Eye Dryness Severity Score and Eye Dryness Frequency Score on mITT and PP populations will be performed by imputing missing data using MCMC MI methodology with repeated 25 times of imputation under the assumption of missingness at random. Last observation carried forward (LOCF) method and Fully Conditional Specification multiple imputation (FCS MI) with 200 burn-in iterations and 25 times of imputation under the assumption of missingness at random will be used for sensitivity analyses (Section 4.7.2). LOCF method will be used for sensitivity analyses.

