4.7. Efficacy Evaluation

The efficacy summaries and analyses will be presented for both study and non-study eyes for Cohort 2 only.

The Primary efficacy analysis of the Schirmer test will be conducted using the mITT and PP populations. All the efficacy parameters, with the exception of categorical Schirmer test evaluation (i.e., \geq 10 mm increase in Schirmer) and the categorical BCVA evaluation (i.e. Loss of 3 lines of vision), will be analyzed as continuous variables. Their absolute values at each timepoint (Visit 1, Visit 2, Baseline, Visit 3, Visit 4, Visit 5, Visit 6, Visit 7, Visit 8, and 30-Day Follow-Up), and change from baseline to each post-baseline visit will be summarized using descriptive statistics (the number of subjects, mean, SD, median, minimum and maximum) by treatment group and overall. The number and percentage of subjects with \geq 10 mm increase from baseline in Schirmer test and loss of 3 lines of vision based on BCVA at each post-baseline visit will be tabulated by treatment group and overall. The results for 30-Day Follow-Up visits will be reported only for observed data.

4.7.1. **Primary Analyses**

For the primary efficacy endpoint analyses of Schirmer Test change from baseline, the following modeling and analyses will be performed on MCMC MI of mITT population:

A linear model with fixed effects of treatment (four individual formulations) and baseline Schirmer test value as covariate will be used to compare different formulations in terms of Schirmer Test change from baseline at Visit 7 (Week 12) and all other post-baseline visits (Visit 3, Visit 4, Visit 5, Visit 6, and Visit 8). In the linear model, least square means treatment group comparison of CSI Formulation 1 to HV Formulation 2B, CSI Formulation 2A to HV Formulation 2B, CSI Formulation 1 to HV Formulation 3, CSI Formulation 2A to HV Formulation 3, will be reported. This model will also be used to compare overall OTX-CSI (combined Formulation 1 and Formulation 2A using sample size weights of Formulation 1 and Formulation 2A as coefficients for the parameters in least square means treatment group comparison) to each HV Formulation (2B and 3). Unadjusted treatment group analyses using two-sample t-test will be run on these treatment group combinations.

These analyses will also be performed on the PP population.

Sponsor:	Ocular Therapeutix, Inc.		
Protocol:	CLN-Protocol-0054		
Document Version No.:	V1.0 Document Date:		01-OCT-2021

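### The pooling code for the multiply imputed ANCOVA and t-tests omits the complete-data degrees of freedom, so pooled intervals are slightly too narrow: about 1% for the primary ANCOVA and 1 to 3% for the t-test differences

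*SAP*

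**What the plan says.** SAP 4.2.9.1 sets out imputation, analysis and pooling. On the number of imputed datasets it says "This process of imputation will be repeated 25 times"; the estimates "will be combined using PROC MIANALYZE". It gives no rule for the degrees of freedom of the pooled inference.

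The primary model in SAP 4.7.1 is "A linear model with fixed effects of treatment (four individual formulations) and baseline Schirmer test value as covariate". In the code of 7.3.5 this is "MODEL CHG=TRPG1N base", fitted separately for each visit and imputation. The resulting estimates go to "PROC MIANALYZE DATA=LSMESTIMATEs; modeleffects estimate; stderr stderr". The unadjusted t-test in 7.3.4 is pooled with "proc mianalyze data=ttest2; modeleffects mean; stderr stderr; by AVISITN CLASS". Each call passes only an estimate and its standard error.

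On the error rate, SAP 4.2.1 states: "All statistical testing will be done at the two-sided alpha level of 0.05". SAP 4.2.6 makes no adjustment for multiple endpoints.

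**The concern.** Rubin's original degrees of freedom depend only on the number of imputations and the fraction of missing information. With 25 imputations and modest missingness they run from hundreds to thousands, more than a trial of about 140 subjects can supply. The reference quantile is then close to 1.96, when the complete-data analysis would use about 1.98 (ANCOVA) or 2.00 (40 v 20 t-test).

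The error always makes intervals shorter and p-values smaller. It recurs across six group contrasts and six post-baseline visits for each endpoint analysed on imputed data. The LOCF and observed-data runs in SAP 4.7.2 need no pooling and use t quantiles on finite residual degrees of freedom. Part of any difference between the imputed and unimputed p-values would therefore come from this convention and not from the missing data.

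**Working it through.** The plan states no degrees of freedom, power or missingness figure, so there is no figure of its own to reproduce.

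**Inputs from the documents**
- m = 25 imputations (SAP 4.2.9.1); two-sided alpha 0.05 (SAP 4.2.1).
- Cohort 2 of about 140 subjects, 40/40/40/20 (SAP 2.1).
- ANCOVA with four group means plus a baseline slope: 5 mean parameters, so ν_com = 140 − 5 = 135. All contrasts come from this one model and share this value.
- t-tests use only the two groups compared: 40 + 40 − 2 = 78 and 40 + 20 − 2 = 58. Combined OTX-CSI gives 80 + 40 − 2 = 118 against Formulation 2B and 80 + 20 − 2 = 98 against Formulation 3.

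**Assumptions**
- Fraction of missing information λ = (1 + 1/m)B/T, where B is the between-imputation variance and T the total variance. It is not in the documents; the range taken is 0 to 0.2, with 0.5 as an extreme.
- Without EDF=, the pooling procedure takes ν_com as infinite. This is standard software behaviour, not something the SAP says.

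**Formulas**
- Default: ν = (m − 1)/λ².
- Barnard-Rubin: ν_obs = (1 − λ)·ν_com(ν_com + 1)/(ν_com + 3), and 1/ν_adj = 1/ν + 1/ν_obs.
- Narrowing = 1 − t(0.975, ν)/t(0.975, ν_adj).
- True alpha = 2·P(t with ν_adj df > t(0.975, ν)).

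**Worked case: ANCOVA, λ = 0.10**
- ν = 24/0.01 = 2,400, quantile 1.9610.
- ν_obs = 0.9 × 135 × 136/138 = 119.7.
- ν_adj = 1/(1/2,400 + 1/119.7) = 114.0, quantile 1.9810.
- Narrowing = 1 − 1.9610/1.9810 = 1.01%; true alpha 0.0523.

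**ANCOVA across the range (ν_com = 135)**

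| λ | Default df | Barnard-Rubin df | Quantiles | Too narrow by | True alpha |
|---|---|---|---|---|---|
| 0 | infinite | 133.0 | 1.9600 / 1.9780 | 0.91% | 0.0521 |
| 0.05 | 9,600 | 124.7 | 1.9602 / 1.9792 | 0.96% | 0.0522 |
| 0.10 | 2,400 | 114.0 | 1.9610 / 1.9810 | 1.01% | 0.0523 |
| 0.20 | 600 | 90.4 | 1.9639 / 1.9866 | 1.14% | 0.0526 |
| 0.50 | 96 | 39.3 | 1.9850 / 2.0222 | 1.84% | 0.0542 |

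If the analysed N fell to 100 (ν_com = 95), the narrowing for λ of 0 to 0.2 would be 1.3 to 1.6%, with true alpha at most 0.0537.

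**t-test differences, λ from 0 to 0.2**

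| Comparison | ν_com | Too narrow by | True alpha |
|---|---|---|---|
| 80 v 40 | 118 | 1.0 to 1.3% | 0.0524 to 0.0530 |
| 80 v 20 | 98 | 1.3 to 1.6% | 0.0529 to 0.0536 |
| 40 v 40 | 78 | 1.6 to 2.0% | 0.0537 to 0.0546 |
| 40 v 20 | 58 | 2.2 to 2.7% | 0.0550 to 0.0562 |

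**When a primary conclusion would change.** A result exactly at the corrected critical value is reported by the default as p = 0.0479 at λ = 0 (1.9780 referred to the normal) and p = 0.0474 at λ = 0.2 (1.9866 referred to t on 600 df). Only a reported p between about 0.047 and 0.050 would cross the threshold.

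**Simulation of the null ANCOVA.** Settings: 40/40/40/20, assumed baseline correlation 0.5, m = 25, and 20,000 trials at each of 5%, 10% and 20% missing. For Formulation 1 against 2B and against 3, type I error was 0.0486 to 0.0536 with the default and 0.0468 to 0.0512 with EDF=135. The Monte Carlo standard error is about 0.0015. This agrees with a small excess; at 5% missing the default rates (0.0508 and 0.0486) cannot be told apart from 0.05.

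**The case against.** The strongest reply is that this hardly matters. The trial is Phase 1/2, has no formal sample size calculation and deliberately leaves multiplicity uncontrolled. An excess of 0.2 to 0.3 percentage points per ANCOVA test does not alter what such a design can conclude. That stands as a limit on severity. It does not make the listed code right.

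A second reply is that the listing may be a template and not production code: it shows one t-test pair only, and AVAL9 is used but missing from the variable list. But no other section supplies a degrees-of-freedom rule, so nothing in the SAP corrects the omission.

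Three stronger readings are tempting and are not supported:
- A reader might infer that primary comparisons with the 20-subject Formulation 3 arm suffer most. They do not: every ANCOVA contrast uses the same residual degrees of freedom. The arm-size effect exists only in the pairwise t-tests, which SAP 4.7.1 describes as unadjusted analyses.
- A reader might carry the alpha of 0.055 to 0.056 over to the primary result. Those figures belong to the 40 v 20 t-test alone.
- A reader might conclude that imputed and observed-data results cannot be compared. A quantile difference of about 1% does not go that far, and the two already differ for substantive reasons, such as the subjects included and the between-imputation variance.

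**Conclusion.** The point holds as a minor error in the SAP's own analysis code. The direction is certain given the default behaviour of the pooling procedure: pooled inference is slightly anti-conservative. For the primary ANCOVA the intervals are about 0.9 to 1.1% too narrow and true alpha is about 0.052 to 0.053. For the t-test differences the shortfall is 1.0 to 2.7%, and true alpha reaches about 0.056 in the smallest comparison.

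This rests on N near 140, on an assumed λ of 0 to 0.2, and on the listed code being what is run. At higher λ the default quantile moves away from 1.96, but the shortfall remains (1.8% for the ANCOVA at λ = 0.5). The documents do not support a claim that the primary type I error is materially inflated.

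**What to change.** - **ANCOVA pooling (SAP 7.3.5):** add EDF=N-5, with N the actual number of subjects in the mITT or PP fit (135 at N = 140). The same value serves every least-squares mean and contrast in the call.
- **t-test pooling (SAP 7.3.4):** do not put one EDF= value on the present call. Its input drops only the non-pooled difference rows, so the BY CLASS step also pools single-group means. EDF=n1+n2-2 would credit a 20-subject mean with 58 degrees of freedom when it has 19. Pool the difference rows separately with EDF=n1+n2-2, and the single-group rows with EDF=n-1.
- **Text (SAP 4.2.9.1):** state that pooled inference uses Barnard-Rubin degrees of freedom, with these complete-data values.

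The cost is one option in the ANCOVA call, a split of the t-test call and a sentence of text. No new data are needed and no point estimate or standard error changes. Intervals widen by about 1% for the ANCOVA and 1 to 3% for the t-test differences. Single-group t-test intervals, if reported, widen more. At λ = 0, a 40-subject mean has ν_obs = 39 × 40/42 = 37.1 and quantile 2.026, which is 3.4% above 1.960. A 20-subject mean has 19 × 20/22 = 17.3 and quantile 2.107, which is 7.5% above.

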7.3.6. SAS codes to generate and pool proportions using MI data

```
proc surveyfreq data= pr1fcsy;
            by avisitn imput;
            tables TRPG1*CRIT8 / row ;
            ods output CrossTabs=mi_perc_out;
```

run;

```
proc mianalyze data=mi_perc_out;
    by TRPG1 CRIT8;
    modeleffects RowPercent;
    stderr RowStdErr;
    ods output ParameterEstimates=pooled_percent;
run; quit;
```

7.3.7. SAS codes to generate and pool the Odds Ratio (OR) using MI data

```
ods output ParameterEstimates =OR_out;

proc surveylogistic data= pr1fcsy;

by avisitn imput;

class TRPG1 / param = ref;

model CRIT8 (desc) =TRPG1;

where TRPG1N in (1 3);

run;

proc mianalyze data=OR_out;
```

```
modeleffects Estimate ;
stderr StdErr;
ods output ParameterEstimates=pooled_OR;
```

run; quit;

Sponsor:	Ocular Therapeutix, Inc.			
Protocol:	CLN-Protocol-0054			
Document Version No.:	V1.0	Document Date:	01-OCT-2021	

7.3.8. SAS codes to output 95% CI for proportions using Clopper-Pearson method and 95% CI for the proportion difference using Chan and Zhang (1999) method using observed and LOCF data

ods output RiskDiffCol1=RiskDiffCol1 FishersExact=FishersExact;
proc freq data=adoe;

table TRPG1N* CRIT8 / fisher;

exact riskdiff(method=score);

run;

7.3.9. SAS codes to designate study eye randomly in a case both eyes have the same total corneal fluorescein staining score

- 1- Create a SAS dataset RND1 with 1000 observations,
- 2- Create a variable named FOCID. The first 500 observation with value of "OD" (Right Eye) the last
- 500 observation with value of "OS" (Left Eye)
- 3- Generate a random number using RANUNI (Uniform distribution)
- 4- Sort this dataset by random variable ****;

data rnd1;

```
do i=1 to 500;
FOCID="OD";
rand=ranuni(54603);
output;
end;
do i=501 to 1000;
FOCID="OS";
rand=ranuni(54603);
output;
end;
run;
proc sort data=rnd1(drop=i); by rand; run;
data rnd1; set rnd1; VSORT= n ; run;
proc sort data=rnd1; by VSORT; run;
****
5- Sort the subject by using 2 variables
```

```
a- date of randomization for randomized subjects / date of informed consent for open label subjects
```

- b- random number
- c- subject number

Sponsor:	Ocular Therapeutix, Inc.			
Protocol:	CLN-Protocol-0054			
Document Version No.:	V1.0	Document Date:	01-OCT-2021	

6- Then merge this dataset with RND1 and then selected FOCID will be their study eye.****; proc sort data=idsd.suppdm out=dm1(keep=USUBJID QVAL);

where QNAM="RANDNUMB";

by USUBJID;

run;

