2. STUDY DESIGN

2.1. Synopsis of Study Design

This is a randomized, multi-center, double-masked, vehicle-controlled, phase 1/2 clinical study designed to evaluate the safety, tolerability, and efficacy of OTX-CSI (cyclosporine ophthalmic insert) for intracanalicular use for the treatment of subjects with DED. Approximately 145 subjects (290 eyes) will be enrolled in this study at approximately 15 sites in the US.

Subjects will be enrolled in two cohorts. Cohort 1 will be an open-label group consisting of approximately 5 subjects. Cohort 2 will be a randomized, double-masked group consisting of approximately 140 subjects treated with 2 different hydrogel formulations of OTX-CSI and 2 different formulations of hydrogel vehicle inserts (HV). Both eyes will be treated with the same treatment/formulation.

Cohort Number	Number of Subjects	Treatment	Formulation
1 Open-label	5	OTX-CSI	2A
2 Randomized, double-masked	40	OTX-CSI	1
	40	OTX-CSI	2A
	40	HV	2B
	20	HV	3

Cohort 1

Subjects in Cohort 1 will undergo Screening 14 days prior to Insertion/Day 1 (Visit 2) to determine eligibility and eligibility will be re-confirmed at Visit 2 (Insertion/Day 1). The treatment follow-up visits will occur at Week 2 (Visit 3), Week 4 (Visit 4), Week 6 (Visit 5), Week 9 (Visit 6), Week 12 (Visit 7), and Week 16 (Visit 8). All subjects in Cohort 1 will be followed until Week 16 (Visit 8) whether or not an insert is visualized.

Cohort 2

Subjects in Cohort 2 will undergo Screening 14 days prior to Insertion/Day 1 (Visit 2) to determine eligibility. At Visit 2 (Insertion/Day 1) eligibility will be confirmed and subjects who are eligible will be randomly assigned to one of four treatment groups (OTX-CSI Formulation 1, OTX-CSI Formulation 2A, HV Formulation 2B or HV Formulation 3) in a 2:2:2:1 ratio. Should only a unilateral insertion be possible, Visit 2B will occur within 3 days to attempt the insertion again. The treatment follow-up visits will occur at Week 2 (Visit 3), Week 4 (Visit 4), Week 6 (Visit 5),

Sponsor:	Ocular Therapeutix, Inc.			
Protocol:	CLN-Protocol-0054			
Document Version No.:	V1.0	Document Date:	01-OCT-2021	

Week 9 (Visit 6), Week 12 (Visit 7), and Week 16 (Visit 8). All subjects in Cohort 2 will be followed until Week 16 (Visit 8) whether or not an insert is visualized.

[figure not shown]

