4. STATISTICAL METHODS

4.1. Sample Size Justification

No formal sample size calculations were performed. The proposed sample size will allow for initial estimates of efficacy as well as provide for sufficient safety information to be obtained, while still limiting the number of subjects exposed to the IP.

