4.7.3. Secondary Analyses

1. To analyze the efficacy endpoint of percent of eyes with ≥10 mm Increase in Schirmer Test from Baseline at Visit 7 (Week 12) and other Post-Baseline Visits, the logistic regression or Fisher's exact test will be used as described below:

The two groups of Schirmer test (≥10 mm vs <10 mm) will be compared between treatment groups as CSI Formulation 1 to HV Formulation 2B, CSI Formulation 2A to HV Formulation 2B, CSI Formulation 1 to HV Formulation 3, CSI Formulation 2A to HV Formulation 3, will be reported. This model will also be used to compare overall OTX-CSI (combined Formulation 1 and Formulation 2A) to each HV Formulation (2B and 3) using the logistic regression.

The above analyses will be performed on the change from baseline in Schirmer test (\geq 10 mm vs <10 mm) derived based on the imputed Schirmer data using FCS MI (details in section 4.2.9.1) at visit 7 on the mITT and PP populations using the logistic regression and Odds Ratio (OR), 95% confidence interval for OR, and P-value for OR will be reported. In addition, sensitivity analyses will be done using LOCF and observed data and the two groups of Schirmer test (\geq 10 mm vs <10 mm) will be compared between treatment groups using the Fisher's exact test on this endpoint. These analyses will also be performed on all post-baseline visits.

2. To analyze the efficacy endpoints of Eye Dryness Severity and Eye Dryness Frequency, statistical modeling similar to the primary efficacy endpoint analysis (4.7.1) will be performed for each post-baseline visit (Visit 3, Visit 4, Visit 5, Visit 6, Visit 7, and Visit 8)

Sponsor:	Ocular Therapeutix, Inc.		
Protocol:	CLN-Protocol-0054		
Document Version No.:	V1.0 Document Date: 01-OCT-2021		

using the MCMC MI imputed data on the mITT and PP populations. In addition, sensitivity analyses done for the primary efficacy endpoint will also be performed on this endpoint.

3. To analyze the efficacy endpoints of total Corneal Fluorescein Staining (tCFS) and its sub-region, statistical modeling similar to the primary efficacy endpoint analysis (4.7.1) will be performed for each post-baseline visit (Visit 3, Visit 4, Visit 5, Visit 6, Visit 7, and Visit 8) using the MCMC MI imputed data on the mITT and PP populations. In addition, sensitivity analyses done for the primary efficacy endpoint will also be performed on this endpoint.

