5. CHANGES TO PLANNED ANALYSES

The language in the SAP will supersede the language in the protocol should there be a discrepancy.

The primary analysis will be repeated for all visits using observed data (without imputation) for both mITT and PP populations. These results will be provided in sensitivity analyses section.

The difference between two OTX-CSI hydrogel formulations as well as the difference between two HV formulations will not be studied. HV formulations will not be combined.

Wilcoxon rank sum test will be used only to analyze LOCF and observed data.

For Eye Dryness Severity and Eye Dryness Frequency, as well total Corneal Fluorescein Staining (tCFS) and its sub-region the main analysis will be based on MCMC MI and sensitivity analyses will be done using LOCF, observed data, and FCS.

For the first secondary efficacy endpoint analysis, for the main analysis, the two groups of change from baseline in Schirmer test (\geq 10 mm vs <10 mm) at visit 7 will be compared between treatment groups using the logistic regression and for the sensitivity analyses, the groups will be compared using LOCF and observed data by Fisher's exact test; Clopper-Pearson method will be used to calculate 95% confidence interval of the proportion of subject with change from baseline in Schirmer Test \geq 10 mm; to calculate 95% confidence interval of the proportion difference, the Chan and Zhang (1999) method will be used.

These analyses will also be performed on all post-baseline visits.

Sponsor:	Ocular Therapeutix, Inc.		
Protocol:	CLN-Protocol-0054		
Document Version No.:	V1.0 Document Date: 01-OCT		01-OCT-2021

6. **REFERENCES**

American Academy of Ophthalmology Cornea/External Disease Panel. Preferred Practice Pattern[®] Guidelines. Dry Eye Syndrome. San Francisco, CA: American Academy of Ophthalmology; 2018. Available at www.aao.org/ppp. Accessed September 23, 2019.

- Disease in the United States Among Adults Aged 18 Years and Older. Am J Ophthalmol. Oct;182:90-98.
- Perry HD. Dry eye disease: Pathophysiology, classification, and diagnosis. Am J Manag Care. 2008;14:S79-S87.
- Schultz C. Safety and efficacy of cyclosporine in the treatment of chronic dry eye. Ophthalmol Eye Dis. 2014;6:37-42.

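### SAP 7.3.6 pools the imputed responder percentages with a Wald-type standard error, so 95% limits taken from it are too short, and often below zero, when an arm has only a few responders

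*SAP*

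**What the plan says.** The responder endpoint is the first secondary variable in SAP 2.6.1.2. Under 4.7.3 item 1 the responder status for the main analysis is "derived based on the imputed Schirmer data using FCS MI". Section 4.2.9.1 sets the number of imputed datasets: "This process of imputation will be repeated 25 times".

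Section 7.3.6 runs PROC SURVEYFREQ on each imputed dataset and passes the row percentage and its standard error to PROC MIANALYZE ("modeleffects RowPercent"; "stderr RowStdErr"). It saves the result with "ods output ParameterEstimates=pooled_percent". No transformation comes before this step and no adjustment of the limits follows it.

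Section 5 does name an interval for a proportion: "Clopper-Pearson method will be used to calculate 95% confidence interval of the proportion of subject with change from baseline in Schirmer Test" of 10 mm or more. That clause follows the LOCF and observed-data sensitivity analyses, and the heading of 7.3.8 confines the exact methods to those two data types. For the imputed data, 4.7.3 item 1 promises the odds ratio with its 95% interval and p-value. It says nothing about an interval for the percentage.

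Cohort 2 is "approximately 140 subjects treated with 2 different hydrogel formulations of OTX-CSI" and two of vehicle, split 40/40/40/20. Section 4.1 reports no formal sample size calculation and adds: "The proposed sample size will allow for initial estimates of efficacy".

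**The concern.** A raw-scale standard error of a percentage shrinks to zero as the percentage approaches zero. It is therefore least reliable in small arms with few responders. Protocol 7.1 criterion 4c admits screening Schirmer values above 0 and up to 10 mm, so a 10 mm gain at least doubles a value in that range. Low counts are plausible, particularly on vehicle, although the documents do not predict them.

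The trial has no powered hypothesis, so the precision of each arm's estimate matters to a reader. As coded, the sensitivity tables carry a sound exact interval, while the main table for the same arm has either no interval or one that can be too short, negative or empty.

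**Working it through.** **Inputs.** Arms of 40, 40, 40 and 20 (SAP 2.1); 25 imputations (4.2.9.1); 95% intervals (two-sided 0.05, 4.2.1). The documents give no responder rate and no interval for this endpoint, so there is no planned figure to reproduce. Responder rates of 5 to 30% and 10% missing data are assumptions.

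**Formula in 7.3.6.** In each imputed set, SE² = p(1-p)/n × 140/139 (the last factor is SURVEYFREQ's N/(N-1) with N=140). Let W be the mean SE², B the between-imputation variance, and T = W + (1 + 1/25)B. The limits are p ± t√T.

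**No between-imputation variation (B=0).** For 1/20: SE = √(0.05×0.95/20 × 140/139) = 4.89 points, and 5 ± 1.96×4.89 gives -4.6 to 14.6%. Other counts, in percent:

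| Responders | 7.3.6 | Clopper-Pearson | Wilson |
|---|---|---|---|
| 0/20 | 0 to 0 | 0 to 16.8 | 0 to 16.1 |
| 1/20 | -4.6 to 14.6 | 0.1 to 24.9 | 0.9 to 23.6 |
| 3/20 | -0.7 to 30.7 | 3.2 to 37.9 | 5.2 to 36.0 |
| 0/40 | 0 to 0 | 0 to 8.8 | 0 to 8.8 |
| 1/40 | -2.4 to 7.4 | 0.1 to 13.2 | 0.4 to 12.9 |
| 3/40 | -0.7 to 15.7 | 1.6 to 20.4 | 2.6 to 19.9 |

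**When the lower limit is negative.** This happens when p < k/(n+k), with k = 1.96² × 140/139 = 3.87. For n=20 the threshold is 3.87/23.87 = 16.2%, or 3.2 responders. For n=40 it is 3.87/43.87 = 8.8%, or 3.5 responders. So 1 to 3 responders give a negative limit at either size. With 4 the limit is positive (2.4% for 4/20, 0.7% for 4/40).

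**With imputation.** Take n=20 with 1 observed responder and 2 values missing, each imputed as a responder with probability 5% (140/139 factor omitted).
- p = 1.1/20 = 5.5%.
- B = 2×0.05×0.95/400 = 0.000238.
- W = (0.055 - 0.055² - 0.000238)/20 = 0.002587.
- T = 0.002587 + 1.04×0.000238 = 0.002834, so √T = 5.32 points.
- Limits: 5.5 ± 10.4, or -4.9 to 15.9%.

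Imputation noise widens the interval slightly and leaves the fault in place.

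**How often few responders occur (binomial, complete data).** The chance of 1 to 3 responders at true rates of 5%, 10%, 20% and 30% is 0.63, 0.75, 0.40 and 0.11 at n=20. At n=40 it is 0.73, 0.41, 0.03 and 0.00.

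**Coverage of the nominal 95% limits.**
- Complete data, exact: n=20 gives 64%, 88% and 82% at true rates of 5%, 10% and 15%; n=40 gives 87% and 91% at 5% and 10%.
- Simulated, 10% missing, 25 normal-model imputations: about 72 to 90% at n=20 and 85 to 92% at n=40 for rates of 5 to 15%. At n=40 it is 93% at a 20% rate and 94% at 30%; at n=20 it is 93% at 30%.
- At n=40 and a 20% rate, exact complete-data coverage is 90.5% for Wald against 92.8% for Wilson, so part of that shortfall comes from the discreteness of the counts.

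**Zero width.** This needs no responder in any of the 25 sets. With 10% missing it occurred in about 13% of simulated trials at n=20 and a 5% rate. It occurred in 3% or less at n=20 with a rate of 10% or more, and at n=40. With no missing data in the arm, the n=20, 5% figure would be 0.95²⁰ = 36%. The simulated values move by some points with the imputation model. Sharing the residual variance across arms, as the regressions in 7.3.3 do, makes zero width rarer.

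**The case against.** The strongest reply is that no interval for the imputed percentages is planned. Section 4.7.3 item 1 lists what will be reported and gives an interval only to the odds ratio. The table titles mention percentages alone. The heading of 7.3.8 names 95% intervals, while that of 7.3.6 does not. This stands in part: a reader might infer that the main tables will show negative or empty intervals, and no text says so. But if the limits are printed, they are wrong when responders are few. If they are not, the main percentage has no interval, and the pooled standard error is defective either way.

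A reader might also infer that zero width is the usual outcome. It is not; with some missing data, a negative lower limit is much the commoner fault. How the software prints a row with zero variance was not tested.

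Nor do the documents support a low responder rate as expected. At 20% or more the 40-subject arms are barely affected, and mainly the 20-subject HV Formulation 3 arm is at risk.

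Finally, the SAP gives exact intervals for the same arms in the observed and LOCF tables, and the primary endpoint is continuous. Both points limit the harm, but neither supplies a sound interval for the analysis that the SAP calls main.

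**Conclusion.** The point holds as a fault in the coded pooling and a gap in the text. The only precision the code produces for the main responder percentages is a raw-scale Wald-type standard error with its limits. If reported, those limits are negative at the bottom and too short for about 1 to 3 responders in an arm of 20 or 40, and have zero width when no imputed set contains a responder. The coverage loss is material at assumed rates of 5 to 15% and small in the 40-subject arms from 20% upward. All of this rests on assumed responder rates and 10% missingness.

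It would be too strong to say that the endpoint's analysis is invalid. The pooled percentages, odds ratios, p-values and observed and LOCF intervals are not affected, and neither is the primary analysis. This is a modest correction to a secondary endpoint, worth making before unmasking.

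**What to change.** In 7.3.6, keep the pooled percentage and the total variance T from MIANALYZE. Convert both to the proportion scale (divide the percentage by 100 and T by 10,000). Compute the 95% limits as a Wilson interval with effective sample size p(1-p)/T, capped at the arm size and set to the arm size when T is 0. State in 4.7.3 item 1 that this interval accompanies the FCS MI percentages.

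In the worked example, p(1-p)/T = 0.0520/0.002834 = 18.3, and the Wilson limits are 1.0 to 25.4% in place of -4.9 to 15.9%. Simulated coverage of this version is 94 to 97% in the cases with missing data.

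A plus-four adjustment applied before MIANALYZE is not a good substitute, because it changes the reported percentage: 0/20 becomes (0+2)/(20+4) = 8.3%.

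The cost is one data step and one sentence. Intervals become asymmetric and somewhat wider at low rates. They are widest when an arm has no observed responder but a few imputed ones, because the effective sample size then falls well below the arm size.
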